### **1.5.2. 52-week Treatment Period Analysis**

The 52-week Treatment Period Analysis will be performed after all the participants have completed the Week 52 assessments (and Safety Follow-up Period for participants not rolling over into the Maintenance Extension Period) or discontinued from the study before the Week 52 assessments. The analysis will formally evaluate the efficacy (including all the exploratory efficacy endpoints defined by Week 52), PK, PD, and safety of MORF-057 during the 52-week Treatment Period.

The 52-week Treatment Period is the 12-week Induction Period plus the 40-week Maintenance Period. The 40-week Maintenance Period is defined as the time from the Maintenance Period First Dose date recorded on the Study Period Transition eCRF page to the date of last treatment recorded on the EOT eCRF page for the main part of the study for participants rolling over to the Extension Period, or to the

study end date (i.e., the date of the last visit including the SFU visit or last procedure) for participants not entering the Extension Period or who discontinued the study early.

Participants initially randomized into an active MORF-057 treatment group (i.e., Group 1, Group 2, and Group 3 in [Table 3](#)), will receive an active MORF-057 treatment (according to study period and group assignment) for the full 52-week Treatment Period. The cumulative data, including those from the Induction Period, will be used for these groups in the 52-week Treatment Period Analysis. For participants initially randomized into the placebo group during the Induction Period and subsequently switched to an active MORF 057 treatment (i.e., 200 mg Q.D.-E) during the Maintenance Period (i.e., Group 4 in [Table 3](#)), only the data collected during the 40-week Maintenance Period will be included in the 52-week Treatment Period Analysis to assess the effect of MORF-057 treatment, unless otherwise specified. Participants who are randomized into the placebo group during the Induction Period and have discontinued the study treatment before entering the Maintenance Period will not be included in this analysis.

In addition, when the Induction Period analysis is performed, an exploratory analysis for the 52-week Treatment Period may also be conducted for the subgroup of participants who have either completed their Week 52 assessments or discontinued the study by the time the last randomized participant completes their Visit 5 (Week 12) assessments.

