## 1.2. Study Design

This study is a randomized, double-blind, placebo controlled, multicenter, Phase 2b study to evaluate the efficacy and safety of 3 active dose regimens of MORF-057 (as capsule, P.O.) versus matching placebo in study participants with moderately to severely active UC.

Approximately 280 participants will be randomized into the treatment groups in a 1:1:1:1 ratio (i.e., 70 participants per group). The study will enroll participants who are advanced therapy naïve (i.e., have no previous exposure to an advanced therapy treatment for UC) and advanced therapy experienced (excluding vedolizumab), with at least 30% but no more than 40% of advanced therapy experienced participants. Randomization stratification factors will include baseline MES (<3 vs 3) and previous use of advanced therapy treatment (advanced therapy naïve vs advanced therapy experienced). All participants will be enrolled from approximately 150 centers worldwide. For this study, moderately to severely active UC will be defined as having an mMCS of 5 to 9 (inclusive), with an MES  $\geq 2$  (confirmed by central reader).

The main part of this Phase 2b study will consist of a Screening Period (up to 6 weeks, consisting of Stage 1 and Stage 2 testing), a Treatment Period (52 weeks, including a 12-week Induction Period and a 40-week Maintenance Period), and a Safety Follow up (SFU) Period (4 weeks).

During the main part of this study, there will be approximately 11 scheduled study visits: Screening Visit(s) (Visit 1 at Weeks 6 to 1), multiple Treatment Visits (Visits 2-10 at Weeks 0, 2, 6, 12, 18, 24, 32, 42, and 52 [End of Treatment (EOT)]), and an SFU Visit (visit to occur 4 weeks after the last dose of study drug is received, which will be at Week 56 if the full Treatment Period is completed or earlier if treatment is discontinued early). Study Day 1 represents the first day of the Treatment Period (i.e., when the participant will receive the first dose of study drug).

All participants who complete the 52-week Treatment Period will have the opportunity to continue their treatment in a 52-week Maintenance Extension Period.

During the optional Maintenance Extension, there will be 5 scheduled visits: 4 Treatment Visits (Visits 11-14 at Weeks 65, 78, 91, and 104 [EOT]) and an SFU Visit (visit to occur 4 weeks after the last dose of study drug is received, which will be at Week 108 if the full Maintenance Extension is completed or earlier if treatment is discontinued early).

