#### **2.4.3. Handling of Missing Data in Efficacy Analysis**

For analysis of primary and secondary efficacy endpoints and other binary exploratory efficacy endpoints, missing endpoint data will be imputed using a nonresponder imputation (NRI) method, unless otherwise specified. Participants will be considered nonresponders for the NRI analysis if they have missing clinical efficacy data at a time point of interest.

For continuous exploratory efficacy endpoints expressed as change from baseline at Week 12, the primary analysis will use the analysis of covariance (ANCOVA) model for comparing MORF-057 group with the placebo group. Participants who have missing baseline value or the value at Week 12 will be excluded from the analysis. The details are described in Section [4.8.3](#).

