### **52-week Treatment Period Analysis and 104-week Total Treatment Period Analysis**

All proportion-based exploratory efficacy endpoints at Week 52 and Week 104, as outlined in [Table 6](#), will be summarized descriptively by treatment groups. The proportions, along with their corresponding 95% CIs, will be provided for the overall population, by previous use of advanced therapy for UC (naïve vs experienced), by baseline MES score (<3 vs 3), and by baseline mMCS score ( $\leq 7$  or  $> 7$ ). The denominator for calculating the proportions for each treatment group will be the total number of participants in the FAS within that group, except for the group initially randomized to placebo, which will use the total number of participants continuing to the Maintenance Period as the denominator.

In addition, the proportion of participants with symptomatic response and the proportion of participants with partial MCS response, along with the 95%CI, will be summarized by treatment groups at each

scheduled visit up to Week 52 in the 52-week Treatment Period Analysis and up to Week 104 in the 104-week Total Treatment Period Analysis. The summaries will use the following two approaches:

- All randomized: at each visit, proportions for each treatment group will be calculated using the total number of participants in the FAS within that group as the denominator, except for the group initially randomized to placebo, which will use the number of participants continuing to the Maintenance Period as the denominator. Participants with missing data will be considered as non-responders by using the NRI method. The calculations will include the re-allocated EOT visits (See the re-allocation approach in Section 2.3) at that visit.
- As observed: at each visit, the denominator for calculating the proportions will be the number of participants with non-missing assessment at that visit, without including the re-allocated EOT visits and without using the NRI method.

The above summaries for proportions of participants with symptomatic response and partial MCS response will also be provided for the subgroups by previous use of advanced therapy for UC (naïve vs experienced), and by baseline MES score (<3 vs 3), in both 52-week Treatment Period Analysis and 104-week Total Treatment Period Analysis. Line plots showing the proportion ( $\pm$  95% CI) at each of the scheduled visits will be provided for each treatment group, both for the overall population and for the subgroups.

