## 5. INTERIM ANALYSIS

The analysis of the 12-week Induction Period will be performed after all the participants have completed the Week 12 assessments or discontinued the study before the Week 12 assessment, as described in Section 1.5.1. The primary and secondary efficacy endpoints will be formally tested only once, specifically at the time of the Induction Period Analysis. When the Induction Period analysis is performed, an exploratory analysis for the 52-week Treatment Period may also be conducted for the subgroup of participants who have either completed their Week 52 assessments or discontinued the study by the time the last randomized participant completes their Week 12 assessments.

An independent DSMB will review participant safety data and monitor scientific integrity throughout the study. Details related to the DSMB will be clearly delineated in the DSMB Charter.

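### The optional early 52-week look admits participants by completion or discontinuation status, so late-randomized participants can enter only as dropouts and the Week 52 proportions using non-responder imputation come out too low

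*SAP*

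**What the plan says.** SAP section 1.5.2 describes the full 52-week analysis, run once everyone has reached Week 52 or left the study. It then adds an optional exploratory version, to be run with the Induction Period Analysis in the "subgroup of participants who have either completed their Week 52 assessments or discontinued the study by the time the last randomized participant" completes Visit 5. Section 5 repeats the rule: those who have finished Week 52 or "discontinued the study by the time the last randomized participant completes their Week 12 assessments".

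Four other provisions determine what the rule produces:

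- Section 1.2 sets "a Treatment Period (52 weeks, including a 12-week Induction Period and a 40-week Maintenance Period".
- Section 2.4.3 sets the default for binary endpoints: "Participants will be considered nonresponders for the NRI analysis if they have missing clinical efficacy data at a time point of interest".
- Section 4.8.3.1 sets the Week 52 denominator: "The denominator for calculating the proportions for each treatment group will be the total number of participants in the FAS within that group", except that the placebo-start group uses those who continued to maintenance. For symptomatic and partial MCS response by visit it also gives a second version: "As observed: at each visit, the denominator for calculating the proportions will be the number of participants with non-missing assessment at that visit". Section 4.8.3.4 handles symptomatic remission the same way.
- Section 1.5.2 leaves out of the 52-week analysis "Participants who are randomized into the placebo group during the Induction Period and have discontinued the study treatment before entering the Maintenance Period".

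The SAP attaches no entry-date restriction, time-at-risk method or caveat to the early subgroup.

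**The concern.** In the full analysis, having completed or discontinued is a timing trigger that every participant eventually meets, so nobody is selected out. In the early look the same wording becomes an inclusion criterion, and it depends on what happened after randomization. A participant who discontinues is admitted however recently randomized. A participant still on treatment is admitted only if randomized early enough to have reached Week 52. Recent enrollees who are doing well and remain on study are left out, while recent enrollees who stopped are counted, nearly all as non-responders.

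If the look is run, it gives the first group-level Week 52 proportions from the trial. Section 4 treats everything in the plan as defined before database lock, so a predictably low estimate would carry prespecified status without a warning.

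**Working it through.** **Plan's own figure.** The SAP gives none for this subgroup. The only design numbers used are 70 per group and the 12- and 52-week time points.

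**Who can enter.** Let accrual last A weeks. The cut-off is A + 12 weeks after the first randomization. A participant has 52 weeks of follow-up only if randomized by week A + 12 − 52 = A − 40. Anyone randomized in the last 40 weeks of accrual has 12 to 52 weeks of follow-up and can enter only by discontinuing. For any dropout above zero, the dropout share of the subset therefore exceeds the true dropout share. The direction follows from the rule alone.

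**Assumptions for the size (none is in the SAP).** Uniform accrual over A weeks; constant dropout hazard with proportion d gone by Week 52; remission q = 35% among Week 52 completers; all dropouts non-responders. The model is for an active group.

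**Formulas, as shares of a group.**

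- Full follow-up available: e = (A − 40)/A
- Completers: C = e(1 − d)
- Dropouts among those with full follow-up: e·d
- Dropouts among the late-randomized: L = (40/A) × p, where p is the mean of 1 − (1 − d)^(f/52) over follow-up f from 12 to 52 weeks
- NRI rate under the SAP rule: C·q/(C + e·d + L)
- Unselected NRI rate: (1 − d)·q

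**Example, A = 52 and d = 30%.**

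- e = 12/52 = 0.231, C = 0.231 × 0.70 = 0.162, e·d = 0.069
- p = 0.195, so L = (40/52) × 0.195 = 0.150
- Subset = 0.162 + 0.069 + 0.150 = 0.380 of the group, about 27 of 70
- Dropout share = (0.069 + 0.150)/0.380 = 58%, against a true 30%
- NRI rate = 0.1615 × 0.35/0.3804 = 14.9%, against 0.70 × 0.35 = 24.5%

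| d | A (weeks) | Dropout share of subset | NRI rate, SAP rule | Unselected NRI rate | Shortfall (points) |
|---|---|---|---|---|---|
| 30% | 52 | 58% | 14.9% | 24.5% | 9.6 |
| 30% | 78 | 42% | 20.3% | 24.5% | 4.2 |
| 30% | 104 | 38% | 21.8% | 24.5% | 2.7 |
| 20% | 52 | 44% | 19.7% | 28.0% | 8.3 |
| 20% | 78 | 29% | 24.7% | 28.0% | 3.3 |
| 20% | 104 | 26% | 25.9% | 28.0% | 2.1 |

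**Check with other inputs.** With A = 78, d = 25% and q = 40%, the formula gives 25.7% against 30.0% unselected. Simulation gives 25.6% under the SAP rule and 29.9% in a cohort defined by randomization date. Over d from 15% to 35% and A from 52 to 130 weeks, the SAP rule gives 0.57 to 0.96 times the unselected rate; q cancels from this ratio.

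**Denominator.** If the section 4.8.3.1 denominator (all FAS in the group) were applied literally to the early look, ongoing participants would also count as failures. With A = 78, d = 25% and q = 40%, the rate would be 14.6% instead of 30.0%.

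**The case against.** The strongest reply is that little hangs on this look. It is optional and exploratory, Week 52 endpoints are only summarized descriptively, and the full 52-week analysis later replaces it. Section 5 says the primary and secondary endpoints are tested once, at the Induction Period Analysis. All of that stands and limits the importance of the point.

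The scope is limited too. The as-observed summaries and the continuous endpoints do not use NRI, so over-represented dropouts do not lower them by this route. Under section 2.3 a maintenance-period end-of-treatment visit nearer to Week 52 can be re-allocated to Week 52, so a few dropouts may count as responders; this offsets the bias slightly but cannot help someone who stopped during induction. Clinical remission and the endoscopic and histologic endpoints have no as-observed counterpart.

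The size is uncertain. With long accrual and low dropout it is about 2 points, well within the imprecision of such small groups.

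Three stronger readings are tempting and not supported:

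- A reader might infer that this look would drive go/no-go or later dose decisions. The SAP states no such use.
- A reader might infer selection on the efficacy result. Selection is on completion or discontinuation status, which arises after randomization but is not the endpoint.
- A reader might infer a serious distortion between regimens. No between-group test or risk difference is planned at Week 52, and the arithmetic is modest: arms with 20% and 30% dropout and equal completer remission truly differ by 28.0 − 24.5 = 3.5 points, and under the rule by 19.7 − 14.9 = 4.8 (A = 52) or 24.7 − 20.3 = 4.4 (A = 78). The placebo-start group is selected somewhat differently, since only its maintenance-period dropouts count.

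**Conclusion.** The point holds for the NRI proportions of the optional early look. Following the rule as written gives Week 52 proportions that are too low whenever there is any dropout, apart from the small offset from re-allocated visits. Under uniform accrual over 52 to 104 weeks, constant-hazard dropout of 20% to 30% and 35% remission among completers, the shortfall is about 2 to 10 points; the SAP supplies none of these inputs, so the range illustrates the size and does not estimate it. A reader should not extend the conclusion to all Week 52 results, to the primary or secondary tests, or to the later full 52-week analysis. It is a moderate point, worth correcting because the bias is predictable and cheap to remove.

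**What to change.** In sections 1.5.2 and 5, define the early cohort by potential follow-up: FAS participants randomized at least 52 weeks plus the visit window before the cut-off, whatever their status at that date. Later-randomized participants are left out even if they have discontinued. Keep the existing rule that placebo-start participants count only if they continued to maintenance. State that this cohort, and not the whole FAS, is the denominator for the early look.

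The expected dropout share then returns to d and the expected NRI rate to (1 − d)·q.

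The cost is two sentences, no new data and a smaller subset. With 30% dropout the expected size falls from about 27 to 16 of 70 per arm at A = 52 (39% smaller) and from about 41 to 34 at A = 78 (17% smaller). Those removed are almost all late-randomized dropouts, and essentially no Week 52 completers are lost. Where accrual is short, the remaining cohort may be too small to be informative, which is itself worth knowing before deciding to run the look.

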### 1.5.3. 104-week Total Treatment Period Analysis

The 104-week Total Treatment Period Analysis will be performed after all the participants enrolled into the Maintenance Extension have completed the Visit 14 (Week 104) assessments and the Safety Follow up Period or discontinued the study. The analysis will evaluate the exploratory efficacy endpoints at Week 104 as appropriate and the long-term safety of MORF 057 during the 104-week Total Treatment Period.

The 104-week Total Treatment Period consists of the 52-week Treatment Period (see Section [1.5.2](#)) and the 52-week Extension Period (see Section [1.5.3](#)). The 52-week Extension Period is defined as the time from the day after the last day of the 40-week Maintenance Period up to the date of the last visit including the SFU visit or last scheduled procedure during the Extension Period.

Similarly to the 52-week Treatment Period Analysis, in the 104-week Total Treatment Period analysis, for participants initially randomized into an active MORF-057 treatment group, the cumulative data during the 104-week Total Treatment Period, including those from the Induction Period and Maintenance Period, will be used. For participants initially randomized into the placebo group during the Induction Period and subsequently switched to an active MORF-057 treatment during the Maintenance and Extension Periods, only the data during the Maintenance and Extension Periods will be included in this analysis to assess the effect of MORF-57 treatment, unless otherwise specified.

## 1.6. Changes From Planned Analysis in the Protocol

Additional analyses are added in Section [4.8.3.1](#) and Section [4.8.3.4](#) for the following variables:

- Symptomatic response and Partial MCS response at Week 12 and Week 52
- Symptomatic remission at Weeks 2, 6, 12 and 52
- Time to symptomatic remission by Week 12

Morphic Therapeutic, Inc.  
Study Number: MORF-057-202

Statistical Analysis Plan  
Version 1.0, 16SEP2024

- Change from baseline to Week 12 in the mMCS score
- Clinical remission, clinical response, and Corticosteroid-free remission at Week 104

## **1.7. Changes From the Previous Version of SAP**

Not applicable.

## 2. DEFINITIONS AND DATA HANDLING CONVENTIONS

### 2.1. Definition of Baseline

#### 2.1.1. Baseline for Safety Analysis

##### Induction Period Analysis

For safety variables in the Induction Period Analysis, baseline is defined as the last non-missing assessment prior to the first dose of study drug (MORF-057 or placebo).

##### 52-week Treatment Period Analysis and 104-week Total Treatment Period Analysis

For safety variables in the 52-week Treatment Period Analysis and 104-week Total Treatment Period Analysis, baseline is defined as:

- The last non-missing assessment prior to the first dose of study drug, for participants initially randomized into an active MORF-057 treatment group.
- The last non-missing assessment prior to the first dose of maintenance treatment, for participants initially randomized into the placebo group and subsequently switched to an active MORF-057 treatment during the Maintenance/Extension Period.

#### 2.1.2. Baseline for Efficacy Analysis

##### Induction Period Analysis

For the efficacy endpoints in the Induction Period Analysis, baseline value is defined as the last non-missing assessment prior to randomization.

##### 52-week Treatment Period Analysis and 104-week Total Treatment Period Analysis

For efficacy variables in the 52-week Treatment Period Analysis and 104-week Total Treatment Period Analysis, baseline is defined as:

- The last non-missing assessment prior to randomization, for participants who are initially randomized into an active MORF-057 treatment group.
- The last non-missing assessment prior to the first dose of maintenance treatment, for participants initially randomized into the placebo group and subsequently switched to an active MORF-057 treatment during the Maintenance/Extension Period.

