### **1.5.1. Induction Period Analysis**

The Induction Period Analysis will be performed after all the participants have completed the Week 12 assessments or discontinued the study before the Week 12 assessments. The analysis will formally evaluate the primary and secondary efficacy endpoints, all the exploratory efficacy endpoints defined by Week 12, and safety of MORF057 vs placebo during the 12-week Induction Period. The PK and PD data during the 12-week Induction Period will also be summarized.

The 12-week Induction Period is defined as the time from the date of randomization to the Induction Period Last Dose date recorded on the Study Period Transition electronic case report form (eCRF) for participants continuing to the Maintenance Period, or the study end date (i.e., the date of the last visit including the SFU visit or last scheduled procedure) for participants who have discontinued the study before entering the Maintenance Period.

If participants continue to the Maintenance Period, they should complete all the Visit 5 (Week 12) assessments before starting their maintenance treatment according to the protocol. However, a small number of participants were observed to deviate from the protocol by starting their maintenance treatment shortly before completing all the Visit 5 (Week 12) assessments. In such cases, all efficacy assessments, clinical laboratory tests, vital signs and electrocardiogram (ECG) collected at Visit 5 (Week 12) will still be included in the analyses for the 12-week Induction Period, even if they are measured after the participants start their maintenance dose. The PK and PD samples collected at Visit 5 (Week 12) for these participants will be handled in the Induction Period Analysis according to the rules specified in Section 2.7 and Section 2.8. Any adverse events that occur after the date of last induction treatment dose will not be included in the Induction Period Analysis. If both the last induction treatment dose and the first maintenance treatment dose occur on the same day, any adverse events reported on that day will be considered for the Maintenance Period and not included in the Induction Period Analysis, unless there is evidence to confirm that the events occurred before the administration of the maintenance treatment.

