For participants initially randomized into the placebo group during the Induction Period and subsequently switched to MORF-057 treatment (i.e., 200 mg Q.D.-E) during the Maintenance Period, unless otherwise specified, only the data collected during the Maintenance Period will be used in the 52-week Treatment Period Analysis to evaluate the effect of MORF-057 200 mg Q.D.-E. The data will be presented in the treatment group denoted by 200 mg Q.D.-E.

The data for the 104-week Total Treatment Period Analysis (see Section 1.5.3) will be presented by treatment groups similar to the 52-week Treatment Period Analysis described above, unless otherwise specified. All data during the 104-week Total Treatment Period will be used in the analysis for participants initially randomized to an active MORF-057 treatment group, and only the data during the Maintenance and Extension Periods will be used for participants initially randomized to placebo and subsequently switched to MORF-057 for maintenance treatment.

Unless otherwise specified, only scheduled visits including re-allocated visits (EOT or unscheduled visits, as described in Section 2.3) will be included in all by-visit analyses of efficacy and safety data. For the group of participants initially randomized to placebo and subsequently switched to MORF-057 for maintenance treatment, only the visits after Visit 5 (week 12) will be included in the by-visit analyses for the 52-week Treatment Period Analysis and the 104-week Total Treatment Period Analysis.

Data that are not summarized will be listed only. All data will be listed as collected for all randomized participants and will be ordered by randomized treatment group and visit if applicable.

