## 4.8. Efficacy Analysis

Unless otherwise specified, all efficacy endpoints will be analyzed based on the FAS.

In the analyses stratified by the randomization stratification factors (baseline MES [ $<3$  vs  $3$ ] and previous use of advanced therapy treatment [advanced therapy-naïve vs advanced therapy-experienced]), any participant who was randomized under the wrong stratum by mistake will be analyzed according to the actual stratum the participant belongs to, unless otherwise specified.

The 12-week Induction Period Analysis will include the primary efficacy endpoint, secondary efficacy endpoint, and all exploratory efficacy endpoint defined by Week 12, comparing MORF-057 versus placebo. As specified in Section 1.5, if participants start their maintenance treatment before completing the efficacy assessment at Visit 5 (Week 12) due to a protocol deviation, the efficacy data collected at Visit 5 (Week 12) will still be included in the analyses for the 12-week Induction Period, even if they are measured after the participants start their maintenance dose..

The 52-week Treatment Period Analysis will include all exploratory efficacy endpoints defined at Week 52, and the 104-week Total Treatment Period Analysis will include all exploratory efficacy endpoints defined at Week 104. All those exploratory endpoints will be summarized descriptively by treatment groups.

In the analyses for the 52-week Treatment Period and the 104-week Total Treatment Period, for participants randomized to the treatment group with placebo as the induction treatment and MORF-057 200 mg Q.D.-E as the maintenance treatment, they will be presented in the treatment group denoted by 200mg Q.D.-E. Summaries for this group will be based on the participants randomized to the placebo group during the Induction Period who have subsequently continued to the Maintenance Period. The denominator for calculating the proportions for this group will be the number of participants continuing to the Maintenance Period, unless otherwise specified. In all by-visit summaries and plots, only visits after Visit 5 (Week 12) will be presented for this group.

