## 6. APPENDICES

### 6.1. Calculation of Stool Frequency and Rectal Bleeding Subscores

Stool frequency and rectal bleeding subscores at baseline and post-baseline visits will be calculated based on a reference date determined as follows:

- For baseline, the reference date is the randomization date.
- For post-baseline visits, the reference date is:
  - The earliest of the visit date recorded on eCRF form, the start date of bowel preparation (if performed), or the date of endoscopy procedure, if the endoscopy procedure is performed at the visit.
  - The visit date recorded on the eCRF If no endoscopy procedure is performed at the visit.

The calculation of stool frequency and rectal bleeding subscores will use the 3 most recent consecutive days of completed diary entries (both stool frequency and rectal bleeding data must be non-missing on the same day) within the past 7 days from the reference date. If 3 consecutive days of completed diary entries are not available, then use the 4 most recent nonconsecutive days of completed diary entries within the 7-day period prior to the reference date. If there are fewer than 3 consecutive days or 4 nonconsecutive days of completed diary entries available, then the subscores are set to missing.

In the calculations of stool frequency and rectal bleeding subscores at baseline, diaries collected on the following days within the 7-day period from the reference date will be excluded:

- Days of bowel preparation
- The day of endoscopy + 2 days

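### The 52- and 104-week efficacy baseline for the placebo-switch group has no rule for a Visit 5 endoscopy or biopsy done after the first maintenance dose, so it falls back to the pre-randomization value

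*SAP*

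**What the plan says.** Section 2.1.2 resets the efficacy baseline for Group 4 in the 52- and 104-week analyses to "The last non-missing assessment prior to the first dose of maintenance treatment, for participants initially randomized into the placebo group". It has no exception for late Visit 5 assessments.

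Section 1.5.1 records that such assessments occurred: "a small number of participants were observed to deviate from the protocol by starting their maintenance treatment shortly before completing all the Visit 5". It gives neither the number nor the arms. Section 4.8 then provides that "the efficacy data collected at Visit 5 (Week 12) will still be included in the analyses for the 12-week Induction Period", and Section 1.5.1 applies this "even if they are measured after the participants start their maintenance dose". Both provisions are confined to the Induction Period Analysis.

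For Group 4, Section 4 says that "only the data collected during the Maintenance Period will be used in the 52-week Treatment Period Analysis to evaluate the effect of MORF-057", here meaning the 200 mg Q.D.-E regimen, and that "only the visits after Visit 5 (week 12) will be included in the by-visit analyses" at 52 and 104 weeks.

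Section 6.1, on the stool frequency and rectal bleeding subscores, says: "For baseline, the reference date is the randomization date". It does not mention Group 4's second baseline at the switch.

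**The concern.** The reset exists so that Group 4's change scores describe time on MORF-057 and not time on placebo. A Visit 5 endoscopy or biopsy taken after the first maintenance dose is barred by Section 2.1.2 from serving as baseline, and no other section lets it back in. The last qualifying value is then the one from before randomization, and the Week 52 or 104 change spans the whole placebo induction period.

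At stake are the Group 4 summaries of clinical response, MCS response, histologic improvement, mucosal improvement and the RHI, NI and Geboes change scores. Membership of the baseline MES and baseline mMCS subgroups in the 52- and 104-week tables may also shift. The SAP writes explicit rules for the same deviation for PK (Section 2.7.2), PD (Section 2.8), adverse events (Sections 1.5.1 and 4.9.1) and Week 12 efficacy (Section 4.8). That makes the silence on the switch baseline look like an omission and not a choice.

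**Working it through.** The SAP gives no figure on this point, so the check traces the rules and then applies the endpoint definitions to invented participants.

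**Rule trace**

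1. Section 2.1.2: a Group 4 value qualifies as the 52/104-week baseline only if it precedes the first maintenance dose. The section does not say whether this is judged by date or by clock time when both fall on one day.
2. Sections 1.5.1 and 4.8: late Visit 5 efficacy values count as Week 12 data, in the Induction Period Analysis only.
3. Tables 1 and 6: endoscopic and histologic endpoints fall at Weeks 12, 52 and 104, while Weeks 2 and 6 carry symptom scores. The previous MES or histology value is therefore the pre-randomization one. This is inferred from endpoint timing, since the Schedule of Activities is not in the SAP. Measures taken at intermediate visits may fall back less far.
4. Table 2: clinical response, MCS response, histologic improvement and mucosal improvement use baseline. Clinical remission, MCS remission, endoscopic improvement, endoscopic remission, histologic remission and mucosal healing do not.

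**Invented participants** (mMCS components in the order MES, stool frequency, rectal bleeding)

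| Case | Before randomization | Late Visit 5 | Week 52 | Baseline as written | Visit 5 as baseline |
|---|---|---|---|---|---|
| A: whole mMCS falls back | 7 (3, 2, 2) | 4 (2, 1, 1) | 4 (2, 1, 1) | 7 − 4 = 3; 3/7 = 43%; bleeding ≤ 1: responder | 4 − 4 = 0: nonresponder |
| B: only MES falls back | 5 (3, 1, 1) | 3 (1, 1, 1) | 3 (1, 1, 1) | 5 − 3 = 2; 2/5 = 40%; bleeding ≤ 1: responder | 3 − 3 = 0: nonresponder |
| C: RHI, improved on placebo | 20 | 14 | 12 | 20 − 12 = 8 ≥ 7: improvement | 14 − 12 = 2 < 7: none |
| D: RHI, worsened on placebo | 14 | 20 | 12 | 14 − 12 = 2 < 7: none | 20 − 12 = 8 ≥ 7: improvement |

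A and B become clinical responders with no change during maintenance. C and D show that the sign of the error depends on what happened on placebo.

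**Size in the group summary**

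The denominator is the number of Group 4 participants entering maintenance (Section 4.8), at most about 70 (Section 1.3). The shift in the rate is k/N for k participants reclassified in the same direction:

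- k = 1: 1/70 = 1.4 points; if only 50 enter maintenance, 1/50 = 2.0 points.
- k = 3: 3/70 = 4.3 points.
- k = 5: 5/70 = 7.1 points.

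A mean change shifts by (k/N) × the placebo-period change in those affected. With k = 3 and the 6-point RHI change of case C (20 − 14), this is 3/70 × 6 = 0.26 points. The values of k are assumptions, because the SAP gives no count.

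**The case against.** **The pre-dose rule is clean.** A baseline taken strictly before treatment cannot contain any drug effect. Section 2.8 takes the same line for Group 4 PD data, treating values after the first maintenance dose as invalid. Section 1.5.1 accepts late values as Week 12 outcomes, which is not the same as accepting them as an untreated baseline. This stands as a trade-off: an older clean value against a recent one taken just after a dose. For endoscopy and histology the older value is the worse choice, because it carries 12 weeks of placebo into a column from which placebo data are meant to be excluded. For safety the argument holds in full. Using post-dose laboratory, vital sign or ECG values as baseline could hide an early drug effect.

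**The number may be zero.** Section 1.5.1 speaks of not completing all Visit 5 assessments. It does not say that endoscopy or biopsy was the late item, or that Group 4 was involved. This stands, and limits the point to a gap in the rule.

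**Stronger readings that the SAP does not support:**

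- A reader might infer that the gap flatters the drug. Case D shows the opposite is equally possible.
- A reader might infer that a baseline mMCS could combine three dates. The two diary subscores share one reference date (Section 6.1), so at most two dates can mix, and only if the composite is built component by component, which the SAP does not state.
- A reader might infer that Section 6.1 contradicts Section 2.1.2 for all of Group 4. There is a reading that reconciles them: Visit 5 is a post-baseline visit with its own reference date, and Section 2.1.2 then selects that computed score as the switch baseline. The text is ambiguous, not shown to be contradictory.
- A reader might infer that late Visit 5 values drop out of the 52-week analysis altogether. The restriction on visits covers by-visit analyses. Late safety values can still enter the worst post-baseline shifts in Sections 4.9.2 to 4.9.4.

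**Conclusion.** The gap is real but minor. Section 2.1.2, applied as written in a situation the SAP says arose in the trial, gives any affected Group 4 participant an endoscopic or histologic baseline from before randomization. Their change-based Week 52 and 104 results then include the placebo period.

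For an individual this can reverse responder status. For the group, each reclassified participant is worth about 1.4 points at N = 70, in either direction. The conclusion assumes that at least one Group 4 endoscopy or biopsy followed the first maintenance dose, and that no endoscopy took place between entry and Week 12.

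The 52- and 104-week endpoints are exploratory and descriptive (Section 4.8). The formal Week 12 tests of clinical remission and clinical response use the randomization baseline and are unaffected.

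**What to change.** 1. In Section 2.1.2, state that for Group 4 the 52- and 104-week efficacy baseline is the Visit 5 (Week 12) value, even if collected shortly after the first maintenance dose, and that the last pre-maintenance value is used only when Visit 5 is missing. This also settles the same-day question.
2. In Section 6.1, state that the randomization reference date applies to the randomization baseline, and that Group 4's switch baseline uses the Visit 5 reference date.
3. Leave the pre-dose safety baseline in Section 2.1.1 as it is.

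The cost is a sentence or two in each of two sections, with no change to the design or to any formal test. The downside is that a few efficacy baselines would be measured shortly after a first maintenance dose. Reporting how many Group 4 participants this concerns would let readers judge its weight.
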